### 7.3 Analyses of Exploratory Objectives of Immunogenicity

The following exploratory antibody titers will be summarized using the same statistical approaches as the primary and secondary immunogenicity endpoints.

Microneutralization (MN) responses: Neutralizing antibody titers specific to vaccine-homologous A and B strain(s) and antigenically-drifted influenza strains, at Days 0 and 28 post-vaccination, as measured by a microneutralization assay. Note: additional time points may also be assessed. Derived/calculated endpoints based on these data will include:

- GMT – defined as the antilog of the mean of the log-transformed neutralizing titer for a given treatment group.
- GMR – defined as the ratio of post-vaccination and pre-vaccination neutralizing GMTs within the same treatment group (designated as GMRPost/Pre).
- SCR – defined as proportion of subjects in a given treatment group with either a baseline reciprocal titer of < lower limit of quantitation (LLOQ) and a post-vaccination reciprocal titer 4-fold higher than the LLOQ, or a baseline reciprocal titer of  $\geq$  LLOQ and a post-vaccination reciprocal titer  $\geq$  4-fold higher than the baseline titer. SCR and corresponding

2-sided exact binomial 95% CIs will be constructed by Clopper-Pearson method. Two-sided 95% CIs for the difference in SPRs between treatment groups will be based on the Newcombe hybrid score. Chi-Square p-value will be derived similarly as above.

- Ratio of GMTs between treatment arms at Day 28 post-vaccination (adjusted for intergroup variation in baseline [pre-vaccination] titers). Note: Same comparisons as HAI antibody titers between treatment arms will be conducted using ANCOVA.
- Proportions of Days 0 and 7 peripheral blood T cell isolates that secrete IL-2, IFN- $\gamma$ , and TNF- $\alpha$  cytokines following in vitro restimulation with HA in subjects selected for cellular immune response monitoring. Analysis of exploratory CMI response endpoints will be performed on approximately 189 subjects from 3 preselected sites (63 subjects per site) and results may be reported as an addendum to the main clinical study report.
- HAI titers, as described above. Proportion of subjects with  $\geq$  2-fold or  $\geq$  4-fold increases in HAI titers among those with low baseline titers (ie, lowest quintile) and corresponding 2-sided exact binomial 95% CIs will be constructed similarly by Clopper-Pearson method.
- Reverse cumulative distribution displays of HAI and MN titers corresponding to the comparisons described above for each virus strain will be produced in which Day 0 and Days 28, 56, 182, and 364 distributions will be displayed separately by treatment group. Note: MN will be assessed at Days 0 and 28 and may include additional time points.

## 8 SAFETY ANALYSES

All safety analyses will be based on the safety population. Adverse events are defined as any unfavorable or unintended change in the physical, psychological, or biochemical condition of the subject. An AE temporally related to participation in the study will be documented whether or not considered related to the test article. This definition includes intercurrent illnesses and injuries, and exacerbations of pre-existing conditions. Stable pre-existing conditions which do not change in nature or severity during the study are not considered AEs; however, these should be collected as part of the medical history. AEs will be considered treatment emergent from the date and time of the first administration of the investigational product.

### 8.1 Analyses of Primary Objectives of Safety

Safety analysis will be descriptive and based on the safety population, defined as all subjects who received a dose of trial treatment. Safety data will be summarized overall and by individual treatment group for solicited short-term reactogenicity events on Day 0-6, all unsolicited AE profile by MedDRA preferred term and SOC, and 1-year MAE, SAE, and SNMC profiles post-injection on Day 0. All AEs, including MAEs, SAEs, and SNMCs, will be tabulated by severity, related (possibly, probably, or definitely vs. non-related per investigator assessment), and severe and related. The number and percentage (with 2-sided exact 95% CI) of subjects in each treatment group with a given term will be summarized. A listing and narratives of SAEs will also be produced. For multiple occurrences of an adverse event in the same subject, a subject will be counted only once, using the most severe or most related occurrence for the summarization by severity or relationship to test article, respectively.

### 8.1.1     Solicited Adverse Events

Solicited AEs for this study are pre-specified in Section 8.1.1 of the protocol and include both injection site reactions (ie, bruising, pain, redness, and swelling) and systemic events (ie, chills, diarrhea, fatigue, headache, joint pain, muscle pain, nausea, oral temperature [for assessment of fever], vomiting) that are reported within seven days following the Day 0 vaccination and are solicited by diary. These events are considered related to the test article and are collected using a severity rating of 0 (Normal), or 1, 2, or 3 (mild, moderate or severe, respectively), using the maximal severity observed for the specific symptom post-vaccination.

Notable exceptions include oral temperature, which is collected as a continuous variable and that uses temperature grade ranges established in the toxicity grading scale (TGS), and events of injection site redness and swelling, which will be measured using a Subject Measurement Tool (Appendix 2). Oral temperature (fever) will be summarized by severity according to regulatory guidance, eg, Normal < 38.0°C, Mild = 38.0 – 38.4°C, Moderate = 38.5 – 38.9°C, Severe > 38.9°C. The Subject Measurement Tool is a transparent acetate sheet imprinted with a set of concentric circles with diameters that correspond to TGS ranges that are also used to assign severity.

**Table 3: Listing of Diary Solicited Events**

Injection Site (local) Events	Systemic Events		
	General	Gastrointestinal	Respiratory/Facial
Pain	Oral temperature	Nausea	Eye redness
Bruising	Chills	Vomiting	Facial swelling
Redness	Muscle pain	Diarrhea	Eyelid swelling
Swelling	Joint pain		Hoarseness
	Headache		Sore throat
	Fatigue		Cough
			Difficulty breathing
			Wheezing
			Chest tightness
			Difficulty swallowing

Note: All events listed will be solicited by diary for 7 days post-dosing. Subjects will report injection site events occurring on the arm where the test article was administered. Events reported outside the solicitation window will be categorized and reported as unsolicited AEs.

**Table 4: Definition of Severity Grading for Adverse Events**

Severity Grade	Definitions for Local Adverse Events		Definitions for Systemic Adverse Events
	Visual Local AE Size Grading Description	Non-Visual Local AE Grading Description	Systemic AE Grading Description
0 – Normal	Reaction size (greatest single diameter) < 2.5 cm	No noticeable symptom	No noticeable symptom or finding
1 – Mild	Reaction size (greatest single diameter) 2.5 to 5.0 cm	Discomfort or tenderness noticeable, but does not interfere with normal daily activities	Mild symptoms or diagnostic observations; intervention not indicated; no interference with normal activity
2 – Moderate	Reaction size (greatest single diameter) > 5.0 to 10.0 cm	Moderate discomfort or tenderness on firm pressure; causes some limitation of normal daily activities	Moderate symptoms or diagnostic observations; some interference with normal activity, not requiring medical intervention
3 – Severe	Reaction size greatest single diameter) > 10.0 cm	Severe pain at rest, pain or tenderness immobilizes the injected limb and prevents normal daily activities	Severe symptoms, significantly disrupts or prevents normal daily activities, generally requires medical attention/intervention

**Table 5: Severity Grade Definition for Solicited Gastrointestinal Adverse Events and Fever**

Severity Grade	Gastrointestinal Adverse Event			Fever
	Nausea	Vomiting	Diarrhea	
0 - Normal	No noticeable symptom	No noticeable symptom	No noticeable symptom	< 38.0
1 – Mild	No interference with activity, or 1 to 2 episodes/ 24-hour period	No interference with activity, or 1 to 2 episodes/ 24-hour period	1 to 3 unformed (loose) stools/24-hour period	38.0 to 38.4
2 – Moderate	Some interference with activity, or > 2 episodes/ 24-hour period	Some interference with activity, or > 2 episodes/ 24-hour period	4 to 5 unformed (loose) stools/24-hour period	38.5 to 38.9
3 - Severe	Prevents daily activity, or requires intravenous hydration	Prevents daily activity, or requires intravenous hydration	≥ 6 loose stools/ 24-hour period, or requires intravenous hydration	> 38.9

The following summaries of solicited AEs will be presented by treatment group as part of the primary analysis of safety:

- Summary of solicited treatment-emergent AEs by the verbatim terms specified in the diary and within the post-vaccination window (Days 0-6).
- Summary of all local/systemic solicited AEs by severity (mild, moderate, severe), and within the post-vaccination window (Days 0-6).

### **8.1.2 Unsolicited Adverse Events**

Unsolicited adverse events are defined as any adverse events occurring within the 7-day window following vaccination and not specifically solicited in the diary, or any solicited event that occurs outside the 7-day diary solicitation period. The number (percentage) of subjects with unsolicited AEs will be summarized by MedDRA SOC and PT. All unsolicited AEs will be assessed for severity (Section 8.1.2 in Protocol) and for causality (Section 8.5 in Protocol).

The following summaries of unsolicited AEs will be presented for all subjects in the Safety Population as part of the primary analysis of safety:

- Overall summary of unsolicited AEs by treatment group (Days 0 - 28).
- A summary by severity (normal, mild, moderate, or severe), MedDRA SOC, PT, and treatment group (Days 0 - 28).
- A summary by relationship (causality) to test article of an AE (unlikely/unrelated, possibly, probably, or definitely) to test article, MedDRA SOC, PT, and treatment group (Days 0 - 28).
- A summary of severe and related (unlikely/unrelated, possibly, probably, or definitely) AEs, MedDRA SOC, PT, and treatment group (Days 0 - 28).
- A summary of any AEs including MAEs, SNMCs and SAEs, by MedDRA SOC, PT, and treatment group (Days 0 - 28).

The final analysis will include the following summaries of unsolicited AEs.

- Overall summary of unsolicited AEs by treatment group (Days 0 - 364).
- A summary by severity (normal, mild, moderate, or severe), MedDRA SOC, PT, and treatment group (Days 0 - 364).
- A summary by relationship (causality) to test article of an AE (unlikely/unrelated, possibly, probably, or definitely) to test article, MedDRA SOC, PT, and treatment group (Days 0 - 364).
- A summary of severe and related (unlikely/unrelated, possibly, probably, or definitely) AEs, MedDRA SOC, PT, and treatment group (Days 0 - 364).
- A summary of any AEs including MAEs, SNMCs and SAEs, by MedDRA SOC, PT, and treatment group (Days 0 - 364).

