8 TRIAL ASSESSMENT OF SAFETY

8.1 Adverse Events

Adverse events (AEs) are defined as any unfavorable or unintended change in the physical, psychological, or biochemical condition of the subject. An AE temporally related to participation in the trial or due to a procedure performed in the trial, will be documented whether or not considered related to the test article. This definition includes intercurrent illnesses and injuries, and exacerbations of pre-existing conditions. Stable pre-existing conditions which do not change in nature or severity during the trial are not considered AEs; however, these should be collected as part of the medical history. AEs will be considered treatment emergent from the date and time of the first administration of the investigational product.

Data concerning all classes of adverse events will be collected at scheduled visits from the time informed consent is obtained on Day 0 through Day 28, inclusive. After these specified days, data concerning MAEs, SNMCs, and SAEs will be collected (see Sections 8.1.5 and 8.2 for details of these AEs), as well as additional information regarding outcomes/resolutions of AEs reported prior that had no stop date recorded. In addition to the scheduled visits, subjects will be instructed to notify the investigator and/or return to the clinic if any severe AE (solicited or otherwise) or event fulfilling the definition of an SAE occurs at any time following vaccination. If at a scheduled or unscheduled visit, symptoms are presented that would require a physical exam to adequately assess potential AEs, the exam should be performed and vital signs collected. Adverse events will be recorded as observed by the investigator, designated personnel, or as provided by the subject on the diary card or during the in-person visit. Full details of the AE (ie, nature, date of onset, and recovery, as well as an assessment of severity, relationship to trial treatment [unsolicited events only], seriousness, treatment, and outcome) will be recorded in the source documentation and captured in the eCRF, and will generally require the investigator(s) causality assessment, except as discussed below.

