8.1.2 Unsolicited Adverse Events

Any AEs reported spontaneously by subjects will be categorized as unsolicited events and Medical Dictionary for Regulatory Activities (MedDRA) coded by system organ class (SOC) and preferred term (PT). Solicited events with an onset after the solicitation period will also be classified as unsolicited AEs. Unsolicited events that occur within 7 days following vaccination should also be recorded in the subject diary. If any Grade 3 unsolicited event is reported during this period, subjects should be encouraged to contact the investigator by telephone. The investigator may request an *ad hoc* clinic visit at his/her judgment, and should enter any Grade 3 unsolicited adverse event reported by telephone in the unsolicited AE eCRF promptly, even if the balance of diary data is not yet available. All unsolicited AEs will be assessed for severity

Approved

(as defined in Section 8.1.2) and for causality (as discussed in Section 8.5), and will be documented in the source documents and captured in the eCRF.

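### SAP 8.1.2 defines unsolicited AEs so that a non-diary event starting from Day 7 through Day 28 fits neither limb, contradicting Protocol 8.1.2 and the SAP's own 28-day endpoint

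*SAP*

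**What the plan says.** The SAP definition (section 8.1.2) has two limbs.

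- Limb 1: "Unsolicited adverse events are defined as any adverse events occurring within the 7-day window following vaccination and not specifically solicited in the diary".
- Limb 2: "or any solicited event that occurs outside the 7-day diary solicitation period".

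The same section lists the tables that use the term. The primary safety set begins with "Overall summary of unsolicited AEs by treatment group (Days 0 - 28" and continues with tables by severity, by relationship, and of severe and related events over the same days. The last table in the list is "A summary of any AEs including MAEs, SNMCs and SAEs, by MedDRA SOC, PT, and treatment group (Days 0 - 28". The final analysis repeats the set, starting with "Overall summary of unsolicited AEs by treatment group (Days 0 - 364".

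The protocol's rule is different. Protocol 8.1.2 states: "Any AEs reported spontaneously by subjects will be categorized as unsolicited events". It sets no time limit, and it treats late diary-type events as an addition to that class. The first 7 days appear there only as a rule about what subjects should also write in the diary. On collection, Protocol 8.1 states: "Data concerning all classes of adverse events will be collected at scheduled visits", running from consent on Day 0 to Day 28. After that, only MAEs, SNMCs and SAEs are gathered.

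SAP 2.1.1 sets a 28-day profile of all AEs as part of the primary safety objective, and SAP 2.2.1 makes the endpoint all AEs, laboratory changes included, from Day 0 to Day 27. SAP 1.4 says the plan follows protocol Version 3.0, and SAP section 13 records no change to the protocol's analyses.

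**The concern.** An event that is not a diary term and starts on Day 7 or later within the all-AE period is neither in the 7-day window nor a solicited event outside it. Taken at its word, SAP 8.1.2 leaves it unclassified.

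Two kinds of event show the gap. One is a rash on Day 12 for which nobody sees a doctor. The other is a laboratory value from the Day 28 sample that rises in grade and reaches Grade 2 or more, which Protocol 8.1.4 makes an AE. Day 28 is the only scheduled safety sample after vaccination.

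The primary safety objective calls for a 28-day all-AE profile, and Protocol 10.4.1.1 asks for it by severity and relatedness. Protocol 1.10 describes this as the first human exposure to Quad-NIV with Matrix-M1. A programmer who builds the flag from the SAP sentence would leave later-onset non-serious events, with no medical visit, out of the tables that carry severity and causality.

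**Working it through.** **1. Classify each kind of event under the two rules.** The 7-day window is taken as Day 0 to Day 6, the solicitation period in SAP 2.2.1 and Protocol 8.1.1.

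| Event | SAP 8.1.2 | Protocol 8.1.2 |
|---|---|---|
| Non-diary term, onset Day 0-6 | Unsolicited (limb 1) | Unsolicited |
| Diary term, onset Day 7 or later | Unsolicited (limb 2) | Unsolicited |
| Non-diary term, onset Day 7-28 | Neither limb | Unsolicited |
| Non-diary MAE, SNMC or SAE after Day 28 | Neither limb, but reported under SAP 8.2 or 8.3 | Unsolicited |

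**2. Count the uncovered days for non-diary terms.**

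- Endpoint window (SAP 2.2.1), Day 0 to Day 27: 28 days. Covered: 7. Uncovered: 28 - 7 = 21, and 21/28 = 75%.
- Table window (SAP 8.1.2), Day 0 to Day 28: 29 days. Uncovered: 29 - 7 = 22, and 22/29 = 76%.

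These are calendar days, not events.

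**3. Look for text elsewhere in the SAP that closes the gap.**

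- SAP 8.1 promises the "all unsolicited AE profile by MedDRA preferred term and SOC". This uses the defined term, so it inherits the definition. The matching sentence in Protocol 10.4.1.1 speaks of all AEs over 28 days.
- SAP 8.1 also says that all AEs will be tabulated by severity, by relatedness, and as severe and related. That sentence has no 7-day limit and contradicts the definition.
- The any-AE table in SAP 8.1.2 could hold these events, but it sits in a list introduced as summaries of unsolicited AEs and is broken down only by SOC, PT and group.
- SAP 8.2 summarizes MAEs and SNMCs and includes them in the overall AE summary. SAP 8.3 lists SAEs. Neither reaches an ordinary event with no medical visit.
- The SAP has a vital-signs section (8.4) but no section on laboratory analysis, so its 8.1.2 tables are the main specified route for laboratory AEs.

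**4. Reproduce the plan's safety figures (SAP 9).** P(at least one) = 1 - (1 - p)^n, and the upper bound with no events = 1 - 0.05^(1/n).

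| n | p | P(at least one) | Upper bound |
|---|---|---|---|
| 135 | 1.7% | 90.1% | 2.19% |
| 155 | 1.5% | 90.4% | 1.91% |
| 310 | 0.8% | 91.7% | 0.96% |

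These agree with the stated >90% and with 2.2%, 1.9% and 1.0%.

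**5. Illustrate the effect on the unsolicited tables alone.** Suppose a share f of onsets of a non-diary event falls on Days 0-6. The rate visible to the literal definition is then f × p, and P = 1 - (1 - f × p)^n. The documents give no value for f, so the range below is an assumption.

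| f | n = 135 | n = 155 | n = 310 |
|---|---|---|---|
| 25% (uniform onset) | 43.7% | 44.1% | 46.2% |
| 50% | 68.4% | 68.9% | 71.1% |
| 75% | 82.3% | 82.7% | 84.5% |

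With the limit removed, f = 100% and the figures in step 4 stand.

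**The case against.** The best reply is that the SAP as a whole does not behave as its definition does. SAP 8.1 has all AEs tabulated by severity and relatedness. The endpoint covers all AEs through Day 27. The 8.1.2 tables run to Day 28 and Day 364, which would be odd for a one-week class. The SAP also says it follows the protocol. On this view the sentence is a slip in drafting, perhaps a garbled form of the protocol's diary-recording rule, and a sensible programmer would include the later events.

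Most of that stands, and it is why loss cannot be asserted. Two parts are weaker. The table windows settle little, because limb 2 already brings late diary-type events into them. And SAP 8.1 shows that the SAP contradicts itself; it does not show which rule governs the flag.

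Two further replies narrow the point. Protocol 10.4.1.1 requires Day 28 laboratory summaries and changes in toxicity grade by group, so a Day 28 laboratory change would still be reported in that form even if absent from the AE tables. And an event such as Bell's palsy, which a reader might offer as an example, is a listed AESI in Protocol Table 4. The SAP endpoint carries AESIs within the one-year MAE, SAE and SNMC follow-up, so it would probably surface there.

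**Conclusion.** The definition in SAP 8.1.2 is wrong as written. It omits non-diary AEs with onset from Day 7 through Day 28, contradicts Protocol 8.1.2, SAP 8.1 and SAP 2.2.1, and is not declared as a change. If it is programmed literally, those events would be absent from the Days 0-28 unsolicited AE tables by severity and relationship. For non-diary terms the gap is 21 of 28 endpoint days.

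A reader might infer more than this, and the documents do not support it:

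- **That the events are lost from the 28-day analysis.** All AE classes are collected through Day 28 and other SAP text calls for them to be tabulated. Loss depends on how the flag was or will be built.
- **That three quarters of events are affected.** The 75% counts days. Without an onset distribution, no share of events can be derived, and the probabilities in step 5 of the working rest on an assumed share.
- **That the final tables miss 364 - 7 = 357 days.** After Day 28 only MAEs, SNMCs and SAEs are collected, by design, and they are reported under SAP 8.2 and 8.3. There are no ordinary later-onset AEs to lose.

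**What to change.** Replace the first sentence of SAP 8.1.2 with the protocol rule. An unsolicited AE is any AE not solicited in the diary, whatever its onset day within the applicable collection period (all AEs through the Day 28 visit; MAEs, SNMCs and SAEs thereafter), plus any diary-listed term with onset on or after Day 7. Program every SAP 8.1.2 table from that one flag.

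SAP section 14.1 describes changes made after unblinding, so Day 28 tables may already exist. The sponsor should confirm which rule they used and rerun them if it was the literal one.

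While editing, reconcile the last day of the all-AE window: Day 27 in the protocol synopsis and SAP 2.2.1, Day 20 in Protocol 3.2.1, and Day 28 in the SAP 8.1.2 tables.

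The cost is one sentence, one derivation flag and a check of any existing output. No new data are needed.

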8.5 Relationship (Causality)

The relationship of an AE to the test article must be assessed and documented by the investigator or a qualified sub-investigator. Based on the criteria described below, the investigator must classify the AE according to the following categories shown in [Table 7](#).

Table 7: Definition of Relationship for Adverse Events

Relationship	Relationship Description
Unrelated / Unlikely	
 May or may not follow a reasonable temporal sequence from administration of the test article; No plausible mechanism based on known or suspected actions of the test article or product class; Readily explained by known characteristics of the subject's clinical state, common intercurrent illnesses, or other treatments administered to the subject.
Possibly	
 Follows a reasonable temporal sequence from administration of the test article; Based on known or suspected actions of the test article or product class, a plausible mechanism could exist; May be reasonably explained by known characteristics of the subject's clinical state, common intercurrent illnesses, or other treatments administered to the subject; but the investigator deems this less likely than test article effect.
Probably	
 Follows a reasonable temporal sequence from administration of the test article; Based on known or suspected actions of the test article or product class, a plausible mechanism could exist; Cannot be reasonably explained by known characteristics of the subject's clinical state, common intercurrent illnesses, or other treatments administered to the subject.
Definitely	
 Follows a reasonable temporal sequence from administration of the test article; Consistent with known actions of the test article or product class; Cannot be reasonably explained by known characteristics of the subject's clinical state, common intercurrent illnesses, or other treatments administered to the subject. May be confirmed by rechallenge (if applicable).

Approved

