## 12.5 Missing, Unused, and Spurious Data

In general, there will be no substitutions made to accommodate missing data points. All data recorded on the eCRF will be included in data listings that will accompany the CSR.

When tabulating AE, Concomitant Medications and Hospitalizations data, partial dates of event onset will be handled as follows:

- If the day of the month is missing, the onset date will be assumed to be the date of the Day 0 vaccination or first of the month, whichever is later, in order to conservatively report the event as vaccine-emergent.
- If the month or year (or both) of the onset date is missing, impute month or year (or both) which makes the imputed date most adjacent to the first dosing date.
- If the onset day and month are both missing, the event onset will be coded to the date of the Day 0 vaccination or 1st January of the year, whichever is later, in order to conservatively report the event as vaccine-emergent.
- A completely missing onset date will be coded as the date of the Day 0 vaccination, unless the end date suggests it could have started prior to this in which case impute the 1st January of the same year as the end date.
- When imputing a start date ensure that the new imputed date is prior to the end date of the AE or med.

A conservative approach will be taken to assess the relationship of an event to test article: if the relationship of an event is missing, it will be considered treatment-related. Missing severity for an AE will not be imputed.

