## 13 CHANGES TO ANALYSES SPECIFIED IN THE PROTOCOL

NA

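### SAP 8.1.2 lists unlikely/unrelated events inside the severe-and-related summary of unsolicited AEs, contradicting the definition of related in SAP 8.1 and the protocol

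*SAP*

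**What the plan says.** SAP 8.1 sets the general rule for safety tables. AEs are to be tabulated by severity and as "related (possibly, probably, or definitely vs. non-related per investigator assessment), and severe and related". Protocol 10.4.1.1 and the statistical methods part of the protocol synopsis use the same wording.

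SAP 8.1.2 then lists the unsolicited AE tables. One bullet asks for "A summary of severe and related (unlikely/unrelated, possibly, probably, or definitely) AEs" by system organ class, preferred term and treatment group. It appears in the Days 0-28 list, which belongs to the primary analysis of safety, and again in the Days 0-364 list for the final analysis. The bullet just above it in each list is "A summary by relationship (causality) to test article of an AE (unlikely/unrelated, possibly, probably, or definitely) to test article", with the same four levels in parentheses.

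Three other places bear on the reading:

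- Protocol 8.5: "the investigator must classify the AE according to the following categories shown in" Table 7, which has four categories (Unrelated / Unlikely, Possibly, Probably, Definitely).
- SAP 12.5: "if the relationship of an event is missing, it will be considered treatment-related".
- SAP 13, headed "CHANGES TO ANALYSES SPECIFIED IN THE PROTOCOL": the entry is NA.

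**The concern.** A table titled severe and related should hold events that pass two filters. The SAP 8.1.2 wording puts the non-related category inside the related set, so the second filter has no content. A programmer who works from 8.1.2, which is the more specific text, and one who works from 8.1 could reasonably produce different tables under the same title.

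Safety is a primary objective, and protocol 10.4.1.1 promises a severe-and-related tabulation. Subjects are 65 or older, so intercurrent illness unrelated to vaccine is to be expected among severe unsolicited events. Under the literal wording those events would be reported under a heading that calls them related.

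**Working it through.** The plan states no figure for this table, so there is none to reproduce. The check compares the sets of causality levels.

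| Place | Levels counted as related |
|---|---|
| Protocol Table 7 (all categories available) | Unrelated / Unlikely; Possibly; Probably; Definitely |
| SAP 8.1, protocol 10.4.1.1, synopsis | Possibly; Probably; Definitely (3 of 4) |
| SAP 8.1.2, both severe-and-related bullets | Unlikely/unrelated; Possibly; Probably; Definitely (4 of 4) |

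**Step 1. Coverage.** Every assessed unsolicited AE falls in one of the four Table 7 categories. An unassessed one counts as related under SAP 12.5. The 8.1.2 list plus missing therefore covers every unsolicited AE.

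**Step 2. Result of the filter.** Severe AND (any of four levels, or missing) = severe. The set selected by the literal wording equals all severe unsolicited AEs.

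**Step 3. Deliberate change?** SAP 13 declares no change from the protocol's analyses, so the four-level list is not a declared redefinition.

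**Step 4. Size, under assumption only.** Let N be the number of severe unsolicited AEs and p the share judged related.

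- Literal count: N
- Count under SAP 8.1: p × N
- Ratio: N / (p × N) = 1 / p

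The documents do not give p. Assumed values: p = 0.10 gives 1 / 0.10 = 10; p = 0.25 gives 4; p = 0.50 gives 2. These are ratios of events. The tables count subjects, so the tabulated ratio could differ.

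**Step 5. The joint condition.** For repeat occurrences SAP 8.1 counts a subject once, taking the worst grade for severity tables and the closest relationship for causality tables. It gives no rule for a table that needs both. Take a subject with one severe unrelated event and one mild, possibly related event under the same preferred term. The two maxima are severe and possibly related. If they are combined, the subject counts as severe and related, although no single event is both. Deleting the stray level does not by itself close this gap.

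**The case against.** The strongest reply is that the bullet means severe AEs displayed by relationship level. Parentheses in SAP 8.1.2 elsewhere list all levels of a variable: the severity bullet names every grade, and the relationship bullet names every causality category. The disputed bullet repeats the latter list, which points to a level list or a copying slip. On that reading the table is not a duplicate of the relationship table, because it is restricted to severe events. The severe-and-related count can be recovered by adding the possibly, probably and definitely columns, provided each subject is placed once, at the most related of the severe occurrences. In addition, SAP 8.1 is the parent section and already defines related.

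Much of this stands. A reader might infer that the severe-and-related information would be lost altogether; the documents do not support that, since a by-level display keeps it. But the SAP does not say that a by-level display is meant. Even if it is, the title is wrong, and the bullet specifies no pooled count to carry the exact 95% CI that SAP 8.1 calls for.

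Two other stronger readings are tempting and should be resisted:

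- **That the defect distorts the main tolerability evidence on Matrix-M1.** SAP 8.1.2 covers unsolicited AEs only. Solicited reactions are presumed related and tabulated separately by severity (protocol 8.1.1, SAP 8.1.1). SAEs have their own listing and narratives. The holding rules rest on Grade 3 solicited events and definitely related SAEs. No test or decision is tied to this table. Unrelated events in randomised arms may dilute a difference but create no systematic false excess.
- **That the overstatement is larger over 364 days.** This is plausible but not shown. Protocol 1.8.1 reports 22 SAEs in 19 subjects of the earlier trial, none assessed as related. Serious is not the same as severe, and that is a different trial, so the figures cannot size this table.

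**Conclusion.** The contradiction is real and occurs in both lists. As written, the SAP 8.1.2 specification does not match its own title, SAP 8.1, protocol 10.4.1.1 or the synopsis. That conclusion is a comparison of sets and rests on no assumed rate.

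Its reach is limited to one descriptive unsolicited-AE table, produced for two periods. Solicited reactions, SAE listings, holding rules, the primary immunogenicity test and the sample size are unaffected. The 10-, 4- and 2-fold overcounts depend wholly on assumed related shares and on the literal reading; under a by-level display only the label and the missing pooled count are at fault. The point should be corrected because the table would otherwise carry a title that its contents may not meet, and the correction is nearly free.

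**What to change.** In both SAP 8.1.2 bullets (Days 0-28 and Days 0-364), delete the unlikely/unrelated level. Add one sentence: severe and related means a single event that is both severe and possibly, probably or definitely related, with missing relationship counted as related per SAP 12.5; the flag is set at event level, and a subject counts once per term if any event carries it.

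Alternatively, retitle the table as severe AEs by relationship, keep all four levels, and add a pooled severe-and-related row derived in the same way.

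The cost is a short edit to two bullets, one added sentence, matching changes to table titles and programs, and a check of any tables already produced. Because the edit restores the protocol's own definition, it is not data-driven even if made after unblinding.
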